3.1 Trial design

The CLOC study aim to include 80,000 participants that will be randomized in a 1:1 ratio to consume 5 ml cod liver oil or placebo (corn oil) with lemon taste per day for 6 months.

The study was organized as an ancillary study of Koronastudien, a cohort study that aims to identify risk factors associated with the community- and workplace acquisition of COVID-19 virus and which also aims to identify risk factors for the progression of the

¹ In Koronastudien, the Norwegian Corona Cohort, 140.000 participants have answered a questionnaire about their use of dietary supplements, demographics, airway symptoms, and risk factors for Covid-19. In univariate analyses, it was found that participants using vitamin D and or cod liver oil were associated with a reduced risk of Covid-19 (OR 0.8, p<0.001) and of serious (hospitalized) Covid-19 with hospitalization (OR 0.3, p=0.07).

disease and to understand the virus and the disease itself. Koronastudien has collected extensive electronic questionnaire data using the University of Oslo web-based solution "Nettskjema". Participants of the CLOC study will be a subgroup of participants in Koronastudien, and relevant data from these participants will be shared among the studies.

The hypotheses are:

Intake of cod liver oil can prevent COVID-19 disease

Intake of cod liver oil can prevent serious COVID-19

Intake of cod liver oil can prevent other airway infections

These hypotheses will be tested in a triple-blinded randomized placebo-controlled study where 80.000 participants will be assigned to cod liver oil or placebo in a 1:1 ratio.

The safety of cod liver oil will be explored.

Finally, it is a separate aim of the study to identify the mechanisms of action of any health effects seen. These will be explored under another SAP.

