3.3 Sample size

The fallback method (<https://www.fda.gov/media/102657/download>) will be used to correct for testing of multiple primary endpoints.

The total alpha (0.05) will be divided among the endpoints, and a fixed sequence for the testing will be maintained. As the testing sequence progresses, a successful test preserves its assigned alpha as "saved" (unused) alpha that is passed along to the next

test in the sequence. This passed-along alpha is added to the assigned alpha of the next endpoint, and the summed alpha is used for testing that endpoint. Thus, as sequential tests are successful, the alpha accumulates for the endpoints later in the sequence; these endpoints are then tested with progressively larger alphas.

Endpoints in testing order with power calculation:

1. Serious COVID-19 (MSIS-confirmed COVID-19 with dyspnoea, hospitalization, or death). (MSIS: Mandatory Norwegian Surveillance System for Communicable Diseases). Assigned $\alpha=0.018$.

Based on the observations in Koronastudien of a 40% reduction in serious COVID-19 in the group reporting use of cod liver oil, and an expected incidence of 0.25%, a power of 70%, 67,000 participants will have to be included for this endpoint.

2. COVID-19 positive PCR (MSIS). Assigned $\alpha=0.03$.

Based on the observations in Koronastudien of a 20% reduction in COVID-19 incidence in the group reporting use of cod liver oil, and an expected incidence of 1%, a power of 70%, 65,000 participants will have to be included for this endpoint.

3. A negative SARS-CoV-2 test (MSIS). Assigned $\alpha=0.001$.

COVID tests (SARS-CoV2-2), real time (RT)-PCR, are mostly obtained because of a suspicion of COVID-19. The number of negative COVID tests from one week after starting taking cod liver oil/placebo and to the end of the intervention period. This endpoint has been added as an alternative to the Positive PCR or bacterial culture endpoint (now a secondary endpoint, as it is not available at this time).

4. Self-reported airway infection. Assigned $\alpha=0.001$.

Based on the expected frequency of airway infections in Koronastudien of >30% and as a threshold of clinically interesting reduction of all airway infections of 10%, 23,000 participants will have to be included for this endpoint. The study has a power for this endpoint >95%. 16,000 participants in the study will give an 80% power for this endpoint.

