 - Any self-reported airway infections during the period from one week after start of cod liver oil/placebo consumption (*deriv_Date_CLO_start_corr*) to June 2, 2021.
 - Self-reported airway infections criteria
 - Variable: *deriv_respinf_date_yn*

- Answered question *has had respiratory infection since last cloc report* in any CLOC questionnaire (R1-R6)
 - *deriv_respinf_report_yn_ever*
- Date of self-reported airway infections in the period from one week after start of cod liver oil/placebo consumption (*deriv_Date_CLO_start_corr*) to June 2, 2021.
 - *deriv_respinf_date_sums*
-
- Supplementary variable
 - *deriv_respinf_count_report_sum*
 - Number of respiratory infections reported
 - *Rx_Date_respiratoryinfectionx_sym_start_report*
 - Date of each infection reported in each report form

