cancer	difference in lung cancer incidence in	of vitamin D in cod
	postmenopausal women (RR 0.90, 95% CI 0.39 to	liver oil lung cancer
	2.08; 3 RCTs, 37601 women; low-certainty evidence).	indidence?

Benefit/Risk Assessment

Based on existing literature and data from Koronastudien, we have identified cod liver oil as a supplement that may prevent Covid-19 and or reduce the severity of the disease and found that the benefit of testing this in a randomized study far outweighs the risks. A full benefit/risk assessment is found in the Ethics section.

3. Objectives and endpoints

Based on the encouraging results from Koronastudien as well as existing evidence from the literature, we aim to investigate whether cod liver oil can prevent Covid-19, serious Covid-19, or other respiratory tract infections.

We also aim to explore and confirm already known health effects and possible new health effects, in particular rare adverse events associated with cod liver oil use. This will be done during a follow-up period of up to two years after the end of the cod liver oil period

We hypothesize that:

Intake of cod liver oil can prevent Covid-19 disease Intake of cod liver oil can prevent serious Covid-19 Intake of cod liver oil can prevent other airway infections

These hypotheses will be tested in a triple-blinded randomized placebo-controlled study where 80.000 participants will be assigned to cod liver oil or placebo in a 1:1 ratio.

The safety of cod liver oil will be explored.

Finally, it is a separate aim of the study to identify the mechanisms of action of any health effects seen.

Definition of endpoints

A. Number of participants diagnosed with serious Covid-19 (primary endpoint)

The number of participants with first time SARS-CoV-2 positive nasopharyngeal and or pharyngeal swabs (or any other sample used for detection of current disease) analyzed by reverse transcriptase quantitative polymerase chain reaction (RT-qPCR) nucleic acid amplification test or antigen tests [18] used by accredited Norwegian microbiology laboratories in the period from one week after the start of cod liver oil/placebo taking to the end of the study period together with any of the following:

A) Self-reported dyspnea concurrent with the positive test

OR

B) self-reported hospitalization caused by Covid-19 concurrent with the positive test OR

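### The third hypothesis concerns other airway infections, but the fourth primary endpoint scores any airway infection, COVID-19 included

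*SAP*

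**What the plan says.** SAP 3.1 lists three separate hypotheses: COVID-19, serious COVID-19, and "Intake of cod liver oil can prevent other airway infections". The objective in protocol section 3 makes the same separation: the oil "can prevent Covid-19, serious Covid-19, or other respiratory tract infections". SAP 2.2 also says *other*.

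The fourth primary endpoint does not carry that word. SAP Appendix 1 defines it as "Any self-reported airway infections during the period from one week after start of cod liver oil/placebo consumption", fed by the questionnaire item "has had respiratory infection since last cloc report". Its sample size in SAP 3.3 rests on a "clinically interesting reduction of all airway infections of 10%, 23,000 participants will have to be included for this endpoint".

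No rule removes participants or episodes with a positive SARS-CoV-2 test from this variable. We looked in SAP 6.1, 6.2 and Appendix 1, and in the protocol's endpoint D and section 9. The pre-specified sensitivity analyses (SAP 6.1 and 6.2) concern compliance only.

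Endpoint 4 starts with alpha 0.001 and can inherit more from earlier successes. SAP 3.3 and SAP 4.1 describe that inheritance differently. In 3.3 a successful test hands its alpha to the next test in line. In 4.1 each test receives its own level plus the levels of all earlier significant tests, whether or not the one just before it succeeded.

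**The concern.** A participant with an MSIS-confirmed COVID-19 illness who reports it as a respiratory infection is a case for endpoint 2 and for endpoint 4. If the oil prevents COVID-19 and nothing else, the two arms still differ on endpoint 4. A significant result could then be written up as prevention of other airway infections, which it would not show.

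The testing scheme adds to this. Endpoint 4 gets appreciable alpha only after an earlier endpoint has succeeded, and the first two are the COVID-19 endpoints. The larger level therefore tends to arrive when a COVID-19 effect has been declared and the overlap carries a difference.

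**Working it through.** **Inputs.** SAP 3.3: COVID-19 1% with a 20% reduction; serious COVID-19 0.25% with a 40% reduction; airway infection 30% (stated as above 30%) with a 10% reduction; alphas 0.018, 0.03, 0.001 and 0.001. SAP 3.1: 80,000 participants, 1:1.

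**Assumptions.** Two-sided tests (sidedness is not stated); no effect on other infections; endpoint 3 a true null, independent of endpoint 4; a share s of COVID-19 cases newly turns endpoint 4 to Yes.

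**1. The plan's own figures.** Per arm, n = [z(α/2)·√(2p̄q̄) + z(β)·√(p₁q₁ + p₂q₂)]² / (p₁ − p₂)². With 0.30 against 0.27, α = 0.001 and 80% power: (3.291 × 0.6384 + 0.842 × 0.6380)² / 0.0009, about 7,731 per arm or 15,462 in total (15,594 with continuity correction). The SAP says "16,000 participants in the study will give an 80% power for this endpoint". Power at 23,000 is 96.0%, in line with the stated >95%. Endpoints 1 and 2 at 70% power give 66,684 and 64,754, against the stated 67,000 and 65,000. One-sided tests at the assigned alphas do not reproduce these sample sizes. The four alphas sum to 0.05.

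**2. The leak.** d = s × (0.010 − 0.008). The upper case is s = 1: every COVID-19 case is reported and none has another scored infection. If every case is reported but a 30% background strikes independently, s = 1 − 0.30 = 0.70. So d = 0.14 to 0.20 percentage points. SE = √(2 × 0.21 / 40,000) = 0.00324, and the mean of z is m = 0.43 to 0.62.

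**3. Rejection of endpoint 4 at a given level a:** Φ(−z(a/2) + m) + Φ(−z(a/2) − m).

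| Level | Reached when (SAP 4.1) | s = 0.7 | s = 1 |
|---|---|---|---|
| 0.001 | no earlier success | 0.22% | 0.38% |
| 0.019 | endpoint 1 only | 3.1% | 4.4% |
| 0.031 | endpoint 2 only | 4.7% | 6.5% |
| 0.049 | endpoints 1 and 2 | 7.0% | 9.3% |
| 0.05 | endpoints 1, 2 and 3 | 7.2% | 9.5% |

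Nearly all the excess is in the direction of benefit: at 0.049 it is 6.2-8.8% against a nominal 2.45%.

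**4. Whole sequence.** Simulated at the design COVID-19 effects, endpoint 1 succeeds in 78.9% of trials, endpoint 2 in 82.9%, and both in 70.6%. That leaves 8.3% with endpoint 1 only, 12.3% with endpoint 2 only and 8.8% with neither.

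*SAP 4.1 wording* (ignoring the 0.001 from endpoint 3):
- no overlap: 0.706 × 0.049 + 0.083 × 0.019 + 0.123 × 0.031 + 0.088 × 0.001 = 4.0%
- s = 0.7: 0.706 × 0.070 + 0.083 × 0.031 + 0.123 × 0.047 + 0.088 × 0.0022 = 5.8%
- s = 1: 0.706 × 0.093 + 0.083 × 0.044 + 0.123 × 0.065 + 0.088 × 0.0038 = 7.8%

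These sums treat endpoint 4 as independent of endpoints 1 and 2. It shares cases with them, so joint simulation gives slightly more: about 6% at s = 0.7 and 8% to 8.5% at s = 1.

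*SAP 3.3 rule.* Endpoint 4 gains alpha only if endpoint 3 is rejected, which is here a false rejection. That happens in 0.706 × 0.049 = 3.5% of trials (endpoint 4 then at 0.05) and 0.123 × 0.031 = 0.4% (then at 0.032). In the other 96.1% endpoint 4 stays at 0.001, apart from a negligible remainder.
- no overlap: 0.0346 × 0.05 + 0.0038 × 0.032 + 0.961 × 0.001 = 0.28%
- s = 0.7: 0.0346 × 0.072 + 0.0038 × 0.048 + 0.961 × 0.0022 = 0.48%
- s = 1: 0.0346 × 0.095 + 0.0038 × 0.066 + 0.961 × 0.0038 = 0.72%

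Joint simulation gives about 0.5% to 0.8% against 0.3%.

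**5. Sensitivity.** If in addition only 70% of cases are reported, s = 0.7 × 0.7 = 0.49 and the SAP 4.1 figure is just under 5%. If COVID-19 incidence were 2% (an assumption), m doubles to 0.86-1.24 and rejection at level 0.049 rises to about 14-23%.

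**6. Power without COVID-19 episodes.** Taking a full percentage point out leaves 29% against 26.1%. 80% power then needs about 16,200 participants, and power at 80,000 exceeds 99.9%.

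**The case against.** The strongest reply is that this is a matter of labelling. The null of endpoint 4 is no effect on any airway infection, and the test keeps its level for that null. The full title speaks of COVID-19 and airway infections without *other*, and the sample size refers to all airway infections. No section assigns the third hypothesis to endpoint 4 alone. Endpoint 3, the count of negative SARS-CoV-2 tests, is a non-COVID measure by construction.

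Most of that stands. A reader might infer that the alpha split is faulty or that endpoint 4's test is inflated. The documents do not support that: the fault lies in the match between endpoint and hypothesis. Endpoint 3 does not repair endpoint 4, however, and the objectives do say *other*.

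A reader might also take the last row of the table as the headline, 7.2-9.5% instead of 5%. That row requires endpoints 1, 2 and 3 all to succeed. With no effect on other infections, endpoint 3 must then be falsely rejected, and all three succeed in only about 3.5% of simulated trials. The proper comparator over the sequence is 4% or 0.3%, depending on the alpha rule, and not 5%.

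Nor is endpoint 4 largely endpoint 2 counted twice. COVID-19 makes up about 1 in 30 of its events, and the leak is at most 0.2 points against a planned effect of 3 points. A result near the planned effect could not come from the overlap.

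Finally, the full questionnaire wording is not in the documents, a Yes needs a valid date, and missing answers count as No. Complete reporting is therefore an upper case.

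**Conclusion.** The mismatch is real and minor. As derived, endpoint 4 cannot by itself carry a claim about other airway infections, because a COVID-19-only effect moves it. That COVID-19 is included is inferred from the unrestricted wording and the absence of any exclusion.

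At the design values, with 70-100% of COVID-19 cases newly scoring Yes and endpoint 3 null, the chance of a false claim rises from 4% to about 6-8.5% under SAP 4.1. Under SAP 3.3 it rises from 0.3% to about 0.5-0.8%. The size therefore depends mainly on which alpha rule applies, and the documents leave that open. It grows with COVID-19 incidence and shrinks with incomplete reporting.

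**What to change.** Before unblinding, choose one of two routes.

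- **Change the endpoint.** In SAP 6.1 and Appendix 1, and in protocol endpoint D and section 9 to match, do not score an episode whose symptom-start date falls within a pre-specified interval around an MSIS-positive test. Other infections in the same person still count. Report the all-infection version as supportive. Changing Appendix 1 alone would leave the SAP at odds with the protocol.
- **Change the claim.** Keep any airway infection as the primary endpoint and reword the third hypothesis and the objectives to match. Pre-specify the analysis without MSIS-positive episodes as the basis for any statement about other infections.

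With either route, reconcile SAP 3.3 and SAP 4.1 on how alpha reaches endpoint 4.

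The cost is one date rule. Appendix 1 already lists the MSIS test date and the date of each reported infection. The drawbacks are that the rule depends on testing, so untested COVID-19 stays in, and that the interval is a judgement to be fixed in advance. The loss of power is negligible.

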Sponsor and contact details

Sponsor: Oslo University Hospital, [name]

Principal Investigator (PI):

[name], PhD Oslo University Hospital, Department of Microbiology, Section of Research [name] Email: [contact] [contact]

Protocol Amendment Summary of Changes Table

DOCUMENT HISTORY			
Document	Date		
1.0: First complete REK approved protocol.	Completed October 5. Approved October 12, 2020		
1.01:	Completed October 22, 2020		
1.02	Completed October 27. 2020		
1.1	Completed November 30, 2020		

1.2	Completed November 10. 2021

Amendment 1 (October 22, 2020)

Use of antigen tests added as these have a very high specificity [18]. Change of full study title: addition of randomized, placebo and airway infections. Follow up period for definition of serious Covid-19 disease changed from 8 to 4 weeks.

Amendment 2 (October 27, 2020)

Norwegian label translated.

Endpoints described according to ClinicalTrials standard Endpoints at 12 months moved from secondary endpoints to exploratory endpoints.

Amendment 3 (November 30, 2020)

We have interpreted the Exclusion criteria about cod liver oil in Caucasians as Caucasians that use vitamin D cannot or cod liver oil 5-7 times per week can not be included, while use of omega 3 only is acceptable for inclusion. This is not directly clear from the text as it is written.

Amendment 4 (November 10, 2021)

Follow up period for definition of serious Covid-19 disease changed from 4 weeks to 'in the period around the positive SARS-CoV-2 test. Removed fever as an endpoint for serious Covid-19 disease. Primary endpoint 'laboratory verified respiratory infections' replaced with 'negative SARS-CoV-2 tests'. *'Laboratory verified respiratory infections' moved to secondary endpoints.*

Study compliance, blood sampling changed from monthly to after 3-4 months after start cod liver oil/placebo.

Simple dietary questions on vitamin D and LCPUFA n-3 food sources at baseline instead of a full FFQ. Definition of compliant participants changed.

Other minor changes.

1. Protocol Summary

Preliminary evidence from literature and an ongoing study in our lab suggests that cod liver oil may prevent Covid-19 and complications of Covid-19. We will investigate whether this is actually the case or in "Transtudien" by randomizing volunteers to take cod liver oil or placebo (corn oil) during the winter months of 2020-2021.

Schema

June-September 2020: Study design and approvals phase September-October 2020: Screening and inclusion of participants October 2020-April 2021: Cod liver oil or placebo taking period November 2020-April 2021: Obtain registry data May 2021: Compiling data and publish results November 2021: End of follow up 2030: End of study.

2035 Destruction of patient list.

2. Introduction

Study Rationale and background

Cod liver oil is an important source of long-chain omega-3 polyunsaturated fatty acids (n-3 LCPUFA), in particular, eicosapentaenoic acid (EPA, 20:5n-3) and docosahexaenoic acid (DHA, 22:6n-3), and vitamin D. It is an important supplement for people who do not eat fatty fish as recommended by the Norwegian authorities. The health benefits of EPA and DHA are well documented, indicating protective effects on cardiovascular disease (CVD) and the immune system [1-4]

Vitamin D acts on nuclear receptors on multiple locations and have a wide range of short- and long term effects, including the prevention of rickets, asthma exacerbations [5], and importantly acute respiratory tract infections [6, 7].

The health effects of a combination of polyunsaturated fatty acids with and without vitamin D have recently been investigated in the VITAL study, which included 25,000 participants over five years. No serious safety concerns were noted, although all-cause mortality remained unchanged [4, 8].

In a recent report from Ernæringsrådet (2018), a Norwegian government agency, it was found that low levels of vitamin D were prevalent in the Norwegian population, and it was recommended that all dairy products and plant-based substitutes should be fortified with vitamin D. Cod liver oil is mentioned in Norwegian official dietary advice as an important source of n-3 LCPUFA.

In the Cod Liver Oil for Covid-19 Prevention study (CLOC), 80.000 participants will be randomized to cod liver oil or placebo, aiming to prevent Covid-19 and its complications.

The study is initiated by Oslo University Hospital and is a collaboration with the University of Oslo, the National Institute of Public Health and is partially financed by Orkla Health.

Cod Liver Oil

Fish oils or fat fish are important sources of vitamin D and n-3 LCPUFA in the diet. Cod liver oil contains 10 ug of vitamin D and 1 g of polyunsaturated fatty acids (DHEA 0,6g and EPA 0,4g) per 5 ml and covers the daily requirements for these nutrients with a low risk of overdosing and with a safety profile established through more than 100 years of use. The supplement is widely used in Norway and abroad, and more than 5 million bottles of "Møllers tran", a widely used brand, are produced each year.

The health effects of cod liver oil have been investigated before, including in a randomized controlled study in Norway [9]. However, to our knowledge, no extensive safety studies have been conducted on cod liver oil. Also, most studies are done on either vitamin D or n-3 LCPUFA, and the health effects of the widely used supplement cod liver oil compared to each of these constituents have, to our knowledge, not been described in randomized studies.

Covid-19

Covid-19, the disease caused by the pandemic SARS-CoV-2 virus in 2020, has infected more than 14 million people worldwide and killed more than 0.6 million (Worlometers.info, July 18, 2020).

The most common cause of death is respiratory failure, and most hospitalized patients need extra oxygen supply, and some need mechanical respiratory support in intensive care units. A prominent hypothesis for the pathophysiology of the SARS-CoV-2 virus is that overreaction from the immune system against the virus – a cytokine storm – is involved in causing the lung damage and the life-threatening complications of the disease [10, 11].

Cod liver oil in Covid-19

Vitamin D supplement has been shown to prevent asthma exacerbations and respiratory tract infections [5, 6]. In particular, people with low levels of vitamin D before supplementation benefited. Furthermore, Vitamin D deficiency has been associated with severe disease outcomes and death in

Covid-19, and several studies are investigating the use of vitamin D to prevent these outcomes in Covid-19 [12-14](ClinicalTrials.org).

However, not all studies on vitamin D and Covid-19 are positive, and a large UK biobank study found no association between vitamin D levels ten years ago and Covid-19[15].

Omega 3 long-chain fatty acids have immunomodulatory effects and have been shown to be possibly beneficial when given to patients with respiratory support in intensive care units[16].

The safety of the low doses of vitamin D and n-3 LCPUFA in cod liver oil has been proven in multiple studies [4, 8, 9].

Thus, current literature support that the low levels of vitamin D found in cod liver oil may be sufficient to mediate a protective effect against respiratory tract infections. However, this has not been shown in randomized studies on Covid-19, and the evidence is not unambiguous.

Literature also supports that n-3 LCPUFA may have some additional benefits in respiratory infections and that cod liver oil has an excellent safety profile.

Koronastudien

In Koronastudien, 140.000 participants have answered a questionnaire about their use of dietary supplements, demographics, airway symptoms, and risk factors for Covid-19.

In univariate analyses, we have found that participants using vitamin D and or cod liver oil were associated with a reduced risk of Covid-19 (OR 0.8, p<0.001) and of serious (hospitalized) Covid-19 with hospitalization (OR 0.3, p=0.07).

These protective effects are also seen in preliminary analyses of cod liver oil alone when age, gender, and contact with Covid-19 patients are included in the analyses (OR 0.6, p=0.02) for Covid-19 disease with dyspnea and OR 0.1, p=0.03 for hospitalized Covid-19 disease.

Other short-term health effects of cod liver oil

Cod liver oil and the major constituents, vitamin D and n-3 LCPUFA, have been investigated for a long list of conditions over many years. They have been found to be safe, but many studies have been underpowered to detect smaller effects on health and many need to be validated in new datasets. Our study will not be powered to make conclusions on health effects of cod liver oil, but as exploratory endpoints validating existing findings the randomized data obtained will be of great value both at the end of the cod liver oil taking period and for up to two years which is the follow up period of the study.

Intervention	Cochrane conclusion	CLOC study relevancy
Omega 3-	Considering this and the fact that omega-3 PUFA	Incidence of new
dementia	cannot be synthesised by humans, omega-3 PUFAs	dementia in cod
	might be a promising treatment option for dementia.	liver oil group.
PUFA (including	Increasing PUFA intake probably slightly reduces	Incidence of
Omega 3)-	risk of coronary heart disease events from 14.2% to	cardiovascular
primary and	12.3% (RR 0.87, 95% CI 0.72 to 1.06, 15 trials, 10,076	diseases in cod
secondary	participants)	liver oil group.
prevention of		
cardiovascular	Increasing PUFA intake probably slightly reduces risk	
disease	of coronary heart disease and cardiovascular disease	
	events, may slightly reduce risk of coronary heart	

In total, 70 Cochrane reviews includes vitamin D and 48 includes omega 3. The most relevant research questions for the CLOC study are:

		1
	disease mortality and stroke (though not ruling out	
	harms), but has little or no effect on all-cause or	
	cardiovascular disease mortality.	
Vitamin D-cancer	There is currently no firm evidence	Incidence of new
prevention	that vitamin D supplementation decreases or	cancer diagnoses in
	increases cancer occurrence	the cod liver oil
	Vitamin D ₃ supplementation decreased cancer	group.
	mortality and vitamin D supplementation decreased	
	all-cause mortality, but these estimates are at risk of	
	type I errors due to the fact that too few participants	
	were examined, and to risks of attrition bias	
	originating from substantial dropout of participants.	
Vitamin D-all-	Vitamin D3 seemed to decrease Because of risks	Does the low dose
cause mortality	of attrition bias originating from substantial dropout	of vitamin D in cod
	of participants and of outcome reporting bias due to	liver oil reduce
	a number of trials not reporting on mortality, as well	mortality?
	as a number of other weaknesses in our evidence,	
	further placebo-controlled randomised trials seem	
	warranted.	
Vitamin D-	There is high quality evidence that vitamin D plus	Other fractures
fractures	calcium is associated with a statistically significant	was not prevented,
	reduction in incidence of new non-vertebral	but no large studies
	fractures. However, there is only moderate quality	on cod liver oil
	evidence of an absence of a statistically significant	exist (Meyer et al
	preventive effect on clinical vertebral fractures.	1999)
Vitamin D-	One trial with 4143 participants	A long-duration
dementia	compared vitamin D3 (400 IU/day) and calcium	study did not find
	supplements to placebo. We found low- to	any effect, but low
	moderate-certainty evidence of no effect	quality evidence
	of vitamin D3 and calcium supplements at any time-	and not combined
	point up to 10 years on overall cognitive function	with omega 3.
	(MD after a mean of 7.8 years -0.1 MMSE points,	Ũ
	95% CI -0.81 to 0.61) or the incidence of dementia	
	(HR 0.94, 95% CI 0.72 to 1.24).	
Vitamin D-lung	Vitamin D + calcium may result in little to no	Does the low dose
cancer	difference in lung cancer incidence in	of vitamin D in cod
	postmenopausal women (RR 0.90, 95% CI 0.39 to	liver oil lung cancer
	2.08; 3 RCTs, 37601 women; low-certainty evidence).	indidence?

Benefit/Risk Assessment

Based on existing literature and data from Koronastudien, we have identified cod liver oil as a supplement that may prevent Covid-19 and or reduce the severity of the disease and found that the benefit of testing this in a randomized study far outweighs the risks. A full benefit/risk assessment is found in the Ethics section.

3. Objectives and endpoints

Based on the encouraging results from Koronastudien as well as existing evidence from the literature, we aim to investigate whether cod liver oil can prevent Covid-19, serious Covid-19, or other respiratory tract infections.

We also aim to explore and confirm already known health effects and possible new health effects, in particular rare adverse events associated with cod liver oil use. This will be done during a follow-up period of up to two years after the end of the cod liver oil period

We hypothesize that:

Intake of cod liver oil can prevent Covid-19 disease Intake of cod liver oil can prevent serious Covid-19 Intake of cod liver oil can prevent other airway infections

These hypotheses will be tested in a triple-blinded randomized placebo-controlled study where 80.000 participants will be assigned to cod liver oil or placebo in a 1:1 ratio.

The safety of cod liver oil will be explored.

Finally, it is a separate aim of the study to identify the mechanisms of action of any health effects seen.

Definition of endpoints

A. Number of participants diagnosed with serious Covid-19 (primary endpoint)

The number of participants with first time SARS-CoV-2 positive nasopharyngeal and or pharyngeal swabs (or any other sample used for detection of current disease) analyzed by reverse transcriptase quantitative polymerase chain reaction (RT-qPCR) nucleic acid amplification test or antigen tests [18] used by accredited Norwegian microbiology laboratories in the period from one week after the start of cod liver oil/placebo taking to the end of the study period together with any of the following:

A) Self-reported dyspnea concurrent with the positive test

OR

B) self-reported hospitalization caused by Covid-19 concurrent with the positive test OR

C) death where the Covid-19 infection was wholly or partly responsible as judged by the death certificate, information from relatives or hospital records (see endpoint in the protocol)

B. Number of participants diagnosed with New Covid-19 (primary endpoint):

The number of participants diagnosed with first time SARS-CoV-2 positive nasopharyngeal and or pharyngeal swabs (or any other sample used for detection of current disease) analyzed by reverse transcriptase quantitative polymerase chain reaction (RT-qPCR) nucleic acid amplification test or antigen tests used by accredited Norwegian microbiology laboratories from one week after the start of cod liver oil/placebo taking.

C. A negative SARS-CoV-2 test (primary endpoint)

Covid tests (SARS-CoV-2), real time (RT)-PCR, are mostly obtained because of a suspicion of COVID-19. The number of negative covid tests from one week after starting taking cod liver oil/placebo and to the end of the intervention period. This endpoint has been added as an alternative to the Positive PCR or bacterial culture endpoint (below, secondary endpoint, which is not available at this time).

D. Number of participants with self-reported airway infection (primary endpoint)

The number of self-reported airway infections in the period from one week after starting taking cod liver oil/placebo to the end of the intervention period.

Secondary endpoints

The testing of secondary endpoints will be described in the Statistical Analysis Plan.

- A) Hospitalization for Covid-19
- B) ICU care for Covid-19
- C) Any admissions to hospital
- D) Infection with each of the mentioned pathogens
- E) Visits at GP for infections
- F) Visits at GP
- G) Laboratory confirmed respiratory tract infection (previous primary endpoint)

G) Number of participants with laboratory confirmed respiratory tract infection (this is a previous primary endpoint, which will be studied later when data from laboratories are available):

An airway sample positive for a respiratory pathogen* (either PCR or culture) in the period from one week after the start of cod liver oil/placebo taking to the end of this period

*Influenza virus (A and B), parainfluenzavirus (1,2,3), metapneumovirus, rhinovirus, coronavirus (non-SARS), Respiratory Syncytial virus, Haemophilus Influenzae, Moraxella Catharralis, Streptococcus Pneumonia, Beta-hemolytic streptococci, Mycoplasma pneumonia, Chlamydophila pneumonia, Enterovirus, Bordetella pertussis. The list can be expanded based on the analyses performed in Norwegian Microbiology laboratories.

Exploratory during follow up of up to two years

- Cardiovascular disease incidence and mortality during the study period or follow up
- Cancer incidence and mortality during the study period or follow up
- All-cause mortality during the study period or follow up
- Fracture of the hip or forearm during the study period or follow up
- Incident dementia during the study period of follow up

Endpoints at six months:

All primary endpoints tested in the final statistical analysis plan will be tested six months after unblinding (the end of the cod liver oil or placebo taking period).

Safety

The safety of the intervention will be followed for two years after the end of the cod liver oil taking period. This will be done by observing all-cause mortality and hospital admissions for major disease groups in the cod liver oil versus the placebo group in Norwegian registries.

4. Study Design

Overall Design

The CLOC study will include 80.000 participants that will be randomized in a 1:1 ratio to consume 5 ml cod liver oil or placebo (corn oil) with lemon taste per day for 6-12 months.

The study will be organized as a ancillary study of "Koronastudien", a cohort study investigating Covid-19. Participants will be a subgroup of participants in Koronastudien, and relevant data from these participants will be shared among the studies.

Koronastudien has collected extensive electronic questionnaire data using the University of Oslo webbased solution "Nettskjema". Koronastudien aims to identify risk factors associated with the community- and workplace acquisition of Covid-19 virus and also aims to identify risk factors for the progression of the disease and to understand the virus and disease themselves.

Scientific Rationale for Study Design

Under the current pandemic with thousands of deaths daily worldwide, there is an urgent need to rapidly identify possibly safe and efficient preventive measures against Covid-19 and the complications of the disease. The study is designed to obtain such evidence in a timely manner without exposing the participants to unnecessary risk.

Justification for Dose

The most commonly used daily dose of cod liver oil is 5 ml and this dose will also be used in the study. This dose has been shown to increase the vitamin D levels of volunteers significantly, and contains the daily requirement of vitamin D in for most adults in Norway.

End of Study Definition

The End of study is defined as the last day of cod liver oil taking in the spring of 2021. (Participants will still be followed after this date.)

5. Study population

Inclusion criteria

Any person >18 years with a Norwegian Personal Identity Number

Exclusion criteria

An electronic questionnaire will be used to collect self-reported data about exclusion criteria.

- History of renal failure or dialysis, hypercalcaemia, severe liver disease (chirrosis), sarcoidosis or other granulomataous disease (Wegener)
- Allergy to fish or corn oil.
- Pregnancy or planned pregnancy before summer 2021
- Vegan diet
- Age >75 years old at inclusion based on the Norwegian Personal Identity Number
- Difficulty of swallowing cod liver oil or other oils
- Previous Covid-19 disease
- For Caucasians only: Use of any supplement containing more than trace amounts of vitamin D or omega-3 fatty acids at inclusion (Vitamin D levels in non-Caucasians living in Norway are frequently low even among those self-reporting using dietary supplements).

 This criteria will be relaxed if too few participants volunteers to the study and only Caucasians that use cod liver oil or an equivalent dietary supplement (with vitamin D) more than 5-7 times per week will be excluded. Furthermore, Caucasians that use supplements with omega-3 fatty acids will not be excluded.

Lifestyle Considerations

No restrictions are required

Recruitment

A large number of participants must be recruited in a short period of time. The following recruitment strategies will be employed:

- 1. The CLOC invitation letter and screening questionnaire will be sent to Koronastudien participants.
- 2. The CLOC study will be announced in media including on social media using text, pictures and video, and participants can volunteer to both studies on the study webpage. Participants recruited this way and not already in Koronastudien must also sign the Koronastudien consent form.

The electronic screening questionnaire will contain items to identify participants with exclusion criteria and will be completed during the same time as the consent form. A semi-automated review of all screening questionnaires will be held, and any uncertainties will be clarified by contacting the respondents before final eligibility is decided and a study number assigned.

Screen Failures

Participants submitting the screening questionnaire and do not meet the study criteria will be reported as screen failures. They will not be assigned a study number and will not be rescreened.

6. Study Intervention

The study intervention is cod liver oil 5 ml daily or placebo (corn oil). Both will have lemon taste.

The cod liver oil will be the same as sold under the "Møllers Tran med Sitronsmak" brand.

Label

FOR CLINICAL TRIALS Mollers Cod liver oil with lemon flavor / corn oil with lemon flavor Dosage 5 ml once a day. Taken with food in the morning. Store in a refrigerator. Responsible for the study is Oslo University Hospital, Department of Microbiology, Section for Research, [name] [contact] www.transtudien.no Keep out of reach of children. Do not take more than the recommended dose. Dietary supplements do not replace a varied diet. Best before the end of September 2022. Numbering: xxx

Preparation/Handling/Storage/Accountability

The treatment oils are produced in colored flasks and will be delivered to participants by ordinary mail at room temperature. After reception, the cod liver oil/placebo should be kept in a refrigerator

for the whole study period for optimal quality and taste. The product should be taken in the morning each day to increase compliance and preferably up to two forgotten doses can be taken together.

The participants will be presented with a way of measuring 5 ml of cod liver oil. At the end of the study each participant will be asked to measure the remaining product and report this.

Measures to Minimize Bias: Randomization and Blinding

Randomization and blinding

